The emotional reactivity computerized task was developed specifically for our protocol with OpenSesame® software. The task looks like a type of stroop task. Instructions are to identify as soon as possible the ink color of the word on the screen matches the meaning of the word, in doing as less as possible mistake. We ask to the participants to press a specific button on the keyboard in the case of the ink color of the word matches the meaning of the word and to press on another button on the keyboard if they don't. We developed the task in 3 similarly but not identical versions with the aim of randomly testing the 3 versions on each participant. Each version lasts 12 minutes and has some particularities such as the colors of the words. We generated 3 versions of the task in the aim to limit the classical habituation effect in participants. Each version is made of 6 blocs in 20 trials that is aiming at progressively increasing the stress level because of an increase of the mental load. Bloc 1¹ and bloc 2 are associated with a low stress, bloc 4 and bloc 5 are associated with a moderate stress and bloc 5 and bloc 6 are associated with a high stress. The increase of the mental load is permitted by slowly decreasing the word presentation time, by putting feed-back, instruction switches, time constraints and lastly, by the necessity to do a dual task.

STAI Y-A / PANAS / CES-D / PSS / CFS / SWLS / ICQ-18	ECG/EGG/EEG/ GSR/PPG/Emwave/ respiratory belt positioning	Resting period (30 minutes, seated, eyes closed)	Reactivity period (during the task, seated)	VAS	Recovery period (30 minutes, seated, eyes closed)
--	---	--	---	-----	---

3h30

The period (24 days) between the first session and the second session (T1-T2) will be considered as the control period. The larger BFB effects than the unspecific effects related to the spontaneous physiological and emotional variations will be verified through the control period. We will measure the parameters of interest before (T1) and at the end of the control period (T2). During the period, the participants will have to answer to online questionnaires (SSQ6, MAIA-2, STAI Y-B, Brief-Cope, BFI-N, CTQ) aiming to examine the psychological profile (social support, interceptive sensitivity, trait anxiety, style of coping, early life events).

The second session (T2), T1 + 24 days, will be similar of the first session. We will use the same questionnaires and will record the same electrophysiological parameters. At the end of the

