[figure not shown]
¹ The bloc 1 will not be included in the final statistical analysis because is considered as a training bloc. This choice in accordance to the potential biases related to the increase of the sympathetic activity at the beginning of the task caused by a simple moving to action following the resting period.

second session, a short training session of the biofeedback [BFB] technique will be done and the software using for the biofeedback training will be supplied to each participant included in the experimental group to allowed to us to practice BFB by their self at home. The installation of the program and the explanations needed for using it, will be done during the second session (T2). The BFB software (Emwave Pro®) includes a photoplethysmography sensor that can be positioned on the earlobe. The participants will have to practice the biofeedback technique the next 24 days (3X5 min/day).

The period (24 days) between the second session and the third session (T2-T3) will be considered as the intervention period. At the end of the second session (T2), the participants will be separated into two inter-subject groups: an experimental group performing BFB technique (3X5 min per day) in the intervention period (T2-T3) and a control group not performing a specific exercise in the intervention period (T2-T3). The first 40 participants (20 IBS / 20 PNES) will be included into the experimental group (BFB training) whereas the last 10 participants (5 IBS / 5 PNES) will be included into the control group (no training). The participants won't be informed of the condition to which they belong. We will measure the parameters of interest before (T2) and at the end of the intervention period (T3). During the intervention period, all the participants will have to answer to online questionnaires (BVAQ-B, LES, DHS) aiming to examine the psychological profile (alexithymia, traumatic events).

The third session (T3), T2 + 24 days, will be similar of the two previous sessions. We will use the same questionnaires and will record the same electrophysiological parameters. Finally, a debriefing will be done at the end of the session for each participant. The session will be considered as the end of the study visit.

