Concerning the online questionnaires: the package 1 is constituted by the SSQ6, the MAIA-2 and the STAI Y-B. The package 2 is constituted by the Brief-Cope, the BFI-N and the CTQ. The package 3 is constituted by the DHS. The package 4 is constituted by the BVAQ-B and the LE

II : Statistical analysis plan

Independent variables

Analysis A:

The participants will be separated into two inter-subject groups:

- An experimental group performing BFB technique in the intervention phase (T2-T3)
- A control group no performing an exercise in the intervention phase (T2-T3)

The participants won't be informed of the condition to which they belong.

Independent variables

- Measurement time (T1 / T2 / T3) intra-subject
- Group (experimental group / control group) inter-subject

Analysis B:

The participants will be separated into two inter-subject groups performing by a cluster analysis (HF or RMSSD) in the first session (T1):

- A dysfunctional neurovegetative profile (low vagal tone + low vagal flexibility) group
- A functional neurovegetative profile (high vagal tone + high vagal flexibility) group

The participants won't be informed about their neurovegetative profile. We will include all the participants.

Independent variable

- Neurovegetative profile (dysfunctional profile / functional profile) inter-subject

Analysis C:

The participants will be separated into two inter-subject groups performing by a cluster analysis (HF or RMSSD) in the first session (T1):

- A dysfunctional neurovegetative profile (low vagal tone + low vagal flexibility) group
- A functional neurovegetative profile (high vagal tone + high vagal flexibility) group

The participants won't be informed about their neurovegetative profile. We will include only the experimental group performing the BFB technique.

Independent variables

- Neurovegetative profile (dysfunctional profile / functional profile) inter-subject
- Measurement time (T2 / T3) intra-subject

Dependent variables

Physiological variables:

ECG –HRV:

- HF (0.15-0.40 Hz – high frequency) frequency-domain parameter
- LF (0.04-0.15 Hz – low frequency) frequency-domain parameter
- LF-0.1 Hertz (0.075-0.108Hz - spectral power of the low-frequency 0.1Hz band) frequency-domain parameter
- LF/HF (ratio of LF to HF power) frequency-domain parameter
- Total power (total power of the 0-0.40 Hertz band) frequency-domain parameter
- RMSSD (root mean square of successive RR interval differences) temporal-domain parameter

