- In the case of a failure to respect the conditions for parametric test application, we would make a data transformation to jointly improve normality and homogeneity residues. If the normality is failed and the homogeneity is respected, we would execute non-parametric tests.
- Analysis will be done on the subjects included. Analysis concerning the reactivity period (during the task) will be performed on the all blocs excepted the bloc 1².
- Main and secondary judgment criterions analysis will be performed by parametric tests or by non-parametric tests depending on the conditions for application:

• *Analyse A:*

- An ANOVA to repeated measurement with an intra factor (measurement time: T1 / T2 / T3) and an inter factor (group: experimental / control) on the physiological and psychological data collected.
- Student's test for independent samples will be performed on the psychological scores collected in the second session (T2) to account for the initial level of psychological states between the 2 groups.

² The bloc 1 will not be included in the final statistical analysis because is considered as a training bloc. This choice in accordance to the potential biases related to the increase of the sympathetic activity at the beginning of the task caused by a simple moving to action following the resting period.

- Contrasts will then be made by group on the scores in order to specify the effect of the condition on the physiological and psychological data.
- *Analyse B:*
 - K means non-hierarchical clustering will be performed with K = 2. To categorise participants depending on their resting neurovegetative profile (low vagal tone / high vagal tone) and on their dynamical neurovegetative profile (low vagal flexibility / high vagal flexibility), two K means non-hierarchical clustering will be performed with K = 2. One with HF or RMSSD and one with Δ HF or Δ RMSSD.
 - Student's test for independent samples (dysfunctional neurovegetative profile / functional neurovegetative profile) will be performed on the psychological vulnerability (trait scores) collected.
- *Analyse C:*
 - An ANOVA to repeated measurement with an intra factor (measurement time: T2 / T3) and an inter factor (neurovegetative profile: dysfunctional profile / functional profile) on the physiological and psychological data collected only into the experimental group performing the BFB technique.
- *Correlational analysis:*

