 - Regressions or the Pearson correlations will be performed in order to measure the inter-signal correlation (ECG-EGG-EEG)
 - Regressions or the Pearson correlations will be performed in order to test our hypothesis about the HF/RMSSD related to the "low vagal tone" profile will be more correlated to Δ HF/RMSSD related to the "low vagal flexibility" profile than to Δ HF/RMSSD related to the "high vagal flexibility" profile. As the same as HF/RMSSD related to the "high vagal tone" profile will be more correlated to Δ HF/RMSSD related to the "high vagal flexibility" profile than to Δ HF/RMSSD related to the "low vagal flexibility" profile

Additional analyses

- We will control the age effect and the gender effect.
- Some additional statistical analyses will be exploratory: stability of the resting and the dynamical neurovegetative endophenotypes before the control period (T1) and at the end of the control period (T2).
- Correlation between the LF 0.1Hz and the clinical outcomes.
- To confirm the physiological effects of the BFB (BFB vs pseudo-BFB) on the flexibility of the electrophysiological coupling concerning the brain-visceral axis.

Sample

Power analysis (G * Power; Faul et al., 2007) was performed to determine a priori the sample size needed for this study. The power analysis, for an ANOVA (repeated measures, within-between factors), was performed for an effect size (η_p^2) of .12 with a power of .95 on the main judgment criterion (HRV – vagal tone HF) and reported a necessary sample of at least 22 participants (Kudo et al., 2014; Paul & Garg, 2012; Wells et al., 2012). We decided to include at least 25 IBS patients SII (20 test & 5 control) and 22 PNES patients (20 test & 5 control) in accordance with the possible inclusion rate and the duration of the study.

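### Treatment follows enrolment order (first 20 per diagnosis biofeedback, last 5 control), so Analysis A cannot separate the biofeedback effect from selection or drift over recruitment

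*Combined protocol and SAP*

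**What the plan says.** Part I (Study protocol), in the description of the intervention period, states: "The first 40 participants (20 IBS / 20 PNES) will be included into the experimental group (BFB training) whereas the last 10 participants" are the untrained controls, five with IBS and five with PNES. The split takes effect late ("At the end of the second session (T2), the participants will be separated into two inter-subject groups"), but a participant's group is already determined by enrolment position. The only random element in the documents is the version of the emotional task.

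Part II carries this group into Analysis A. The repeated-measures ANOVA has time (T1/T2/T3) as the within-subject factor and "an inter factor (group: experimental / control) on the physiological and psychological data collected". Contrasts by group are then meant to show what the condition did.

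Three elements might act as safeguards:

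- t tests "on the psychological scores collected in the second session (T2) to account for the initial level of psychological states between the 2 groups" (Statistical analyses, Analyse A).
- "We will control the age effect and the gender effect" (Additional analyses).
- The T1-T2 control period in Part I: "The larger BFB effects than the unspecific effects related to the spontaneous physiological and emotional variations will be verified through the control period".

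**The concern.** Analysis A is the plan's only between-participant comparison of biofeedback with no biofeedback. Every participant meets the three sessions in the same order, so only the control group can separate a biofeedback effect from repeated testing. That works only if the controls are comparable with the trained participants in everything except training.

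Under the sequential rule, controls are the last entrants in each diagnosis. Whatever changes over recruitment (operator experience, season, equipment, case mix) can differ between the groups. Because the next allocation is predictable, the choice of whom to enrol, and when, can also depend on it. Adjusting for enrolment position would not repair this: the groups share no positions within a diagnosis, so the adjustment would be pure extrapolation. A positive group × time result could then reflect biofeedback, selection or drift, and the data could not distinguish them.

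**Working it through.** **1. The plan's own sample size.** Inputs from the Sample section: partial η² = 0.12, power 0.95, α = 0.05. From Analysis A: k = 2 groups, m = 3 times. Assumed because not stated: correlation ρ = 0.5, sphericity. With f² = 0.12/0.88 = 0.136 and λ = f²·N·m/(1−ρ), the interaction F test with (k−1)(m−1) and (N−k)(m−1) degrees of freedom has power 0.944 at N = 20 and 0.964 at N = 22. The stated 22 is reproduced. A between-group main effect would need 66. The same inputs at 40:10 give nominal interaction power of 0.997, so the difficulty is bias and not sample size.

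**2. Separation in enrolment order.** Within a diagnosis, biofeedback takes positions 1-20 (mean 10.5) and control 21-25 (mean 23). The gap is 12.5 of a span of 24, or 0.52. A linear drift of D SD from first to last therefore shifts the group contrast by 0.52·D: 0.26 SD for D = 0.5 and 0.52 SD for D = 1.0.

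**3. Group main effect.** Taking the order overall (mean positions 20.5 and 45.5; gap 25/49 = 0.51), a drift in *level* of 0.5 / 1.0 / 1.5 SD with no treatment effect gives simulated false-positive rates of 14% / 38% / 69%, against about 5% under random 40:10 allocation.

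**4. Group × time.** Here only drift in the *T2-T3 change* matters. Units are SDs of the change score; all drift sizes are assumptions. For a t test of change, 40 v 10:

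- SE = √(1/40 + 1/10) = 0.354 SD, with 48 degrees of freedom.
- Noncentrality = step/SE; for a 0.5 SD step this is 0.5/0.354 = 1.41.

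The planned 2×3 interaction was simulated as F(2,96) with compound symmetry and the shift at T3 only. The gradual-drift rows are simulated for both tests.

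| Scenario, no biofeedback effect | t test of T2-T3 change | Planned group × time |
|---|---|---|
| No drift | 5.0% | 5.0% |
| Step 0.2 SD | 8.6% | 8.1% |
| Step 0.3 SD | 13.2% | 12.4% |
| Step 0.5 SD | 28.3% | 28.2% |
| Step 0.8 SD | 60.2% | 63.0% |
| Gradual 0.5 SD | 10.9% | 10.6% |
| Gradual 1.0 SD | 28.6% | 28.9% |
| Constant level shift 0.8 SD at all three times | cancels | 5.0% |

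**5. Randomised comparison.** With 20/5 randomised within diagnosis (one block of 10 and one of 15, in random order), the t test under gradual drift of 0.5 / 1.0 SD rejects in 4.9% / 4.3%.

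**6. The safeguards.**

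- The T2 t tests cover psychological scores only; the main criterion is HRV (HF).
- Age and gender carry no information on enrolment order.
- Comparing T1-T2 change between groups has a 95% half-width of 2.011 × 0.354 = 0.71 SD and detects a true 0.5 SD step 28% of the time. It cannot see drift confined to T2-T3.

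**The case against.** The strongest reply is that the group main effect is not what the trial relies on. Two of its three time points precede treatment, and the stated sample size matches the interaction. For the interaction, many plausible disturbances act on level and cancel. A linear calendar drift adds the same amount to every 24-day change. A seasonal wave of amplitude A moves level by at most 2A·sin(π·24/365) = 0.41A over 24 days, so if the trained participants average out over the year, a 0.5 SD step needs A of about 0.5/0.41 = 1.2 change-score SDs with every control at the steepest phase. The step scenarios also place the break exactly at the group boundary. This stands: the 28% to 63% step figures are unfavourable cases, and the test is open to bias, not shown to be biased. Selection is likewise possible but not demonstrated, since the documents describe no recruitment procedure.

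A second reply is that the planned contrasts by group could yield the T1-T2 change in each arm, HRV included, and that subtracting it from the T2-T3 change removes drift common to both intervals. That is correct, but the contrasts are not specified as a drift check and the subtraction is imprecise. Under compound symmetry the variance of T3 − 2·T2 + T1 is 6σ²(1−ρ), against 2σ²(1−ρ) for a single change. The half-width therefore grows by √3, to 0.71 × 1.73 = 1.23 change-score SDs.

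Third, the within-person comparison of T1-T2 with T2-T3 does not depend on allocation. True, but it carries session-order effects, which a comparable control group is needed to remove.

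**Conclusion.** The concern holds and should be fixed before the comparison is used. Full confounding of the group main effect with early versus late enrolment follows from the allocation rule and needs no numerical assumption; it takes the bracketed counts as a rule within each diagnosis. For group × time the exposure is conditional: nil for a constant level shift, about 11% and 29% false positives for an assumed gradual drift in the T2-T3 change of 0.5 and 1.0 SD, and higher for a step at the group boundary. Those rates assume 40 v 10, a two-sided 5% level and, for the ANOVA, compound symmetry. No planned safeguard removes the exposure, and no later analysis can restore comparability. Follow-up of the last trained and first control participants may overlap in calendar time, as may recruitment of the two diagnoses; this softens the separation but does not remove it.

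**What to change.** Randomise at the end of T2, after that session's recordings are complete. Keep 4:1 and 20/5 per diagnosis, using a concealed list stratified by IBS/PNES with block sizes varied and not disclosed to recruiting staff. One block of 10 and one of 15 in random order per diagnosis would do; blocks of 5 should be avoided because each holds a single control. The list can be held by existing staff outside recruitment or by a computer system.

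Before the list is drawn, reconcile two statements. The Sample section gives 22 PNES patients but breaks them down as 20 + 5 = 25. Additional analyses refers to pseudo-biofeedback, whereas Part I describes an untrained control.

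If recruitment has already followed the sequential rule, label the Analysis A group comparison non-randomised, make no causal claim from it, and report the T1-T2 change by group, HRV included, with its confidence interval as a drift check.

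The cost is one list, a holder for it and a protocol amendment, with no extra patients or visits. Both conditions must then run throughout recruitment. Randomisation does not cure the imprecision that comes from having only 10 controls.

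### BVAQ-B, LES and DHS are collected only while 40 of 50 participants practise biofeedback; if Analysis B counts them as trait scores, a treatment effect could be mistaken for pre-existing vulnerability

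*Combined protocol and SAP*

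**What the plan says.** Part I (Study protocol) places six online questionnaires in the control period, T1–T2, before anyone has been given the BFB software: "During the period, the participants will have to answer to online questionnaires (SSQ6, MAIA-2, STAI Y-B, Brief-Cope, BFI-N, CTQ". The remaining three come after T2: "During the intervention period, all the participants will have to answer to online questionnaires (BVAQ-B, LES, DHS". Their stated purpose is "aiming to examine the psychological profile (alexithymia, traumatic events".

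During T2–T3 the arms differ. For the treated arm: "The first 40 participants (20 IBS / 20 PNES) will be included into the experimental group (BFB training". For the others: "the last 10 participants (5 IBS / 5 PNES) will be included into the control group (no training".

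Part II (Statistical analysis plan), under Independent variables, defines Analysis B on profiles formed by clustering at T1, with all participants included. Under Statistical analyses, its comparison is a Student's t-test that "will be performed on the psychological vulnerability (trait scores) collected". The instruments that count as trait scores are not named. Arm does not enter the test, and nothing restricts it to scores obtained before BFB. BVAQ-B, LES and DHS appear in the general list of psychological variables, as alexithymia, negative impact, and frequency, severity and intensity scores.

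**The concern.** Analysis B is meant to show whether people with a low-vagal profile are psychologically more vulnerable to begin with. That reading needs scores that the intervention cannot have touched. Six of the nine online questionnaires meet this condition and three do not.

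No baseline value is planned for the three, so the comparison cannot be repaired afterwards by adjusting for a pre-BFB score. A profile difference on them could be a trait difference, a BFB effect, or a mixture. A BFB effect could also hide a real trait difference.

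**Working it through.** **Do the three scales belong to Analysis B?** The plan does not say, so this is an inference.
- Analysis A needs values at T1, T2 and T3, and its t-test needs values at T2. Analysis C needs T2 and T3. The three scales are scheduled once, between T2 and T3, and are not in the session battery. None of these analyses can use them.
- Analysis B is the only planned group comparison left.
- Both online sets are described as measuring psychological profile, whereas the session questionnaires are described as measuring emotional state, life satisfaction and acceptance.
- Alexithymia fits the trait label most readily. LES and DHS are nowhere called traits.

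**The plan's own figure.** The Sample section gives N = 22, which concerns the repeated-measures ANOVA. With f² = 0.12/0.88 = 0.136, 2 groups, 3 times, and assumed correlation 0.5 and sphericity, λ = 0.136 × 22 × 3 / 0.5 = 18.0 on 2 and 40 df. Power is 0.964 (0.944 at N = 20), so 22 reproduces. The plan gives no figure for Analysis B.

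**Exposure.** 40/50 = 80%. The Sample section gives a different total: "at least 25 IBS patients SII (20 test & 5 control) and 22 PNES patients (20 test & 5 control". That is 25 + 22 = 47, although the bracket after the 22 adds to 25. With 47 the share is 40/47 = 85%.

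**Bias.** Let s be the treated share and d the BFB effect in SD units, for the dysfunctional (D) and functional (F) profiles. The spurious difference is

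b = s_D·d_D − s_F·d_F.

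If s_D = s_F and d_D = d_F, then b = 0.

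**Test.** Two-sided t-test at 0.05 (sidedness is assumed), with noncentrality b·√(n₁n₂/(n₁+n₂)). For an assumed 25/25 split the factor is √12.5 = 3.54, on 48 df.

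*Route 1: the BFB effect differs by profile, 80% treated in each.* Then b = 0.8 × (d_D − d_F).

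| Difference in effect (assumed) | b | Rejection, 25/25 | Rejection, 15/35 |
|---|---|---|---|
| 0 | 0 | 5% | 5% |
| 0.2 SD | 0.16 SD | 8.6% | 8.0% |
| 0.5 SD | 0.40 SD | 28.3% | 24.6% |

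*Route 2: the same effect in both profiles, unequal treated shares.* If the 10 controls fall at random between two profiles of 25, the number K in one profile is hypergeometric with variance 10 × 0.5 × 0.5 × 40/49 = 2.04. The difference in treated share is (10 − 2K)/25, with SD 2 × 1.43/25 = 0.114. The worst case, all 10 in one profile, is 10/25 = 0.40.

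| Common effect (assumed) | Average rejection | Worst-case b | Worst-case rejection |
|---|---|---|---|
| 0.2 SD | 5.1% | 0.08 SD | 5.9% |
| 0.5 SD | 5.5% | 0.20 SD | 10.7% |
| 0.8 SD | 6.2% | 0.32 SD | 19.8% |

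**Can adjustment replace re-timing?** An arm term deals with route 2. Route 1 needs an arm-by-profile term, whose unexposed profile contrast rests on the 10 controls. With 5 per profile (assumed) its standard error is √(1/5 + 1/5) = 0.63 SD, against √(1/25 + 1/25) = 0.28 SD for the full comparison.

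**The case against.** The strongest objection is that the case rests on an unstated membership and an unstated effect. The only score that the variable list labels as trait is anxiety on the STAI Y-B, which is collected before BFB. The sponsor may never have meant LES or DHS for Analysis B. This stands as a reason to word the point conditionally and to ask for the list. It does not remove the point, because otherwise the three scales have no planned group comparison.

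A reader might infer that the trial itself expects BFB to act differently by profile, since Analysis C crosses profile with time. The documents do not support that. Analysis C tests such a difference without presuming one, and it cannot include these three scales. It shows only that the question is considered open for other psychological scores.

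It is also fair to say that exposure may be partial, since the readable text does not say when within the 24 days the packages are sent. Recalled events, which LES may partly reflect, may also be hard for BFB to move. Both arguments lower the likely size. Neither makes an in-treatment score equivalent to a pre-treatment one.

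**Conclusion.** The point holds in conditional form. The timing, the 40-to-10 split and the absence of an arm term are in the documents. That the scales are Analysis B trait scores is a strong inference for BVAQ-B and a weaker one for LES and DHS.

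The documents do not support a flat statement that Analysis B is biased on these scales. Bias needs a profile-dependent BFB effect or unequal treated shares. Allocation by order of inclusion does not prevent unequal shares, but by chance alone they matter little. Material inflation comes mainly from the first route. The effect differences, the profile sizes, the equal treated shares and full exposure are all assumptions, and zero bias lies within their range.

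The consequence is limited to at most three scales in one analysis. It deserves a change now because prevention is cheap and later repair is weak.

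**What to change.** - Have BVAQ-B, LES and DHS completed in T1–T2, before BFB starts. Exposure falls from 40/50 to 0/50 and both routes close.
- To limit the added load, move CTQ, which concerns early life events, to T2–T3. If the sponsor thinks that reports of such events could also shift under BFB, keep CTQ where it is and accept the load.
- List by name the scores that Analysis B treats as traits.
- Reconcile the total of 50 in Part I with the 25 + 22 in the Sample section.

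The cost is a re-ordering of online packages that already exist (CTQ would have to be taken out of package 2) and a somewhat heavier questionnaire load in the control period. No new instrument or visit is needed.

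If the timing cannot change, report any of the three scales in Analysis B as descriptive only, with an arm-adjusted sensitivity analysis, and state that 10 controls cannot separate profile from a profile-dependent BFB effect with useful precision.

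### Diagnosis (IBS or PNES) is set by quota but is in no listed test, so the Analysis B trait comparison and the Analysis C profile main effect can reflect diagnosis and not vagal profile

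*Combined protocol and SAP*

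**What the plan says.** The study protocol (Part I, intervention period) sets the diagnosis mix: "The first 40 participants (20 IBS / 20 PNES) will be included into the experimental group (BFB training"), and "the last 10 participants (5 IBS / 5 PNES) will be included into the control group (no training").

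The SAP (Part II, Independent variables) then lists time and group for Analysis A, profile for Analysis B, and profile and time (T2, T3) for Analysis C. The profile factor is "Neurovegetative profile (dysfunctional profile / functional profile) inter-subject". Both diseases are pooled. For Analysis B, "We will include all the participants"; for Analysis C, "We will include only the experimental group performing the BFB technique".

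Under Statistical analyses, profiles are formed from HF or RMSSD and from their change scores: "two K means non-hierarchical clustering will be performed with K = 2". The Analysis B test is unadjusted: "Student's test for independent samples (dysfunctional neurovegetative profile / functional neurovegetative profile) will be performed on the psychological vulnerability (trait scores) collected". Analysis C is a repeated-measures ANOVA with profile as its only between-subject factor.

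Under Additional analyses the one adjustment is "We will control the age effect and the gender effect". Neither that section nor the correlational analyses contain a diagnosis factor, stratum, subgroup or sensitivity analysis.

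**The concern.** IBS and PNES are different conditions, and the plan treats the distinction as important enough to fix by quota. The quotas balance diagnosis between the two training groups. They do not balance it between vagal profiles, because profile is observed and not assigned. If one disease has lower vagal tone and flexibility, it will be over-represented in the dysfunctional profile. If that disease also has different trait scores, the Analysis B t-test will show a profile difference even when profile carries no information within either disease. The trial could then report a psychological vulnerability of the low-vagal profile that a table by diagnosis would have explained. Age and gender adjustment is no substitute, since diagnosis can differ on these measures at the same age and sex.

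**Working it through.** **The plan's own figure.** The Sample section states 22 participants for partial eta squared 0.12 and power 0.95. With f² = 0.12/0.88 = 0.136, k = 2 groups, m = 3 times, and correlation 0.5 and epsilon 1 (both assumed, not stated), λ = f²·N·m/(1 − ρ) = 0.136 × 22 × 3/0.5 = 18.0 on 2 and 40 degrees of freedom. Power is 0.964; N = 20 gives 0.944. So 22 reproduces. It describes the Analysis A layout of two groups by three times, with no diagnosis factor, and does not cover Analysis B.

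**Balance in Analysis A.** IBS share is 20/40 = 50% in the experimental group and 5/10 = 50% in the control group. The difference is zero, so diagnosis does not confound the group contrast if the quotas are met. (The Sample section gives 22 PNES patients beside a breakdown of 20 + 5 = 25; these must be reconciled.)

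**Analysis B: mechanism.** With no profile effect within a disease, the expected spurious profile difference is

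spurious difference = (difference between profiles in the share of one disease) × (trait gap between diseases).

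Both factors must be non-zero.

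**Analysis B: simulation.** Inputs from the plan: 25 IBS and 25 PNES, two one-dimensional K = 2 clusterings (tone and flexibility), alpha 0.05. Assumptions:
- diagnosis shifts tone, flexibility and trait by d SD each;
- tone and flexibility correlate 0.5 within a disease;
- the low/low patients are compared with the high/high patients, which follows the SAP's profile definitions and keeps about 33 to 35 of 50;
- the t-test is two-sided (sidedness is not stated).

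There were 4,000 runs per row.

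| d (SD) | Share difference | Share difference × d | Simulated spurious difference (SD) | Rejection, as planned | Rejection, diagnosis added |
|---|---|---|---|---|---|
| 0.3 | 0.188 | 0.056 | 0.046 | 4.5% | 4.4% |
| 0.5 | 0.304 | 0.152 | 0.157 | 7.0% | 4.6% |
| 0.8 | 0.463 | 0.370 | 0.368 | 16.9% | 4.6% |
| 1.0 | 0.555 | 0.555 | 0.556 | 30.1% | 5.0% |

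The product formula agrees with the simulation to within 0.01 SD. The correlation between tone and flexibility is not in the documents. Taking them as independent within a disease moves the 0.8 and 1.0 SD rows to about 19% and 35%. Across the variants run, the ranges are 17-19% and 30-36%.

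With one link only (0.8 SD on the vagal measures or on the trait, not both), rejection stays at 4.6% to 5.0%.

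**Analysis C.** With two time points, the profile-by-time interaction test is a t-test on the T3 − T2 change. A disease difference that is the same at T2 and T3 cancels from that change. With 20 per disease and a constant shift of 0.3 to 1.0 SD, the interaction rejects in 4.7% to 5.2% of runs. It rises only when the diseases also change differently:
- a 0.5 SD gap in change with vagal gaps of 0.5 and 0.8 SD gives up to about 8% and 10%;
- gaps of 0.8 and 1.0 SD on both vagal measures and change give 14-16% and 26-27%, against about 4-5% with diagnosis adjusted for.

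The profile main effect averages over T2 and T3. A constant disease difference does not cancel there, so it is exposed in the same way as the Analysis B comparison.

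**The case against.** Four objections carry weight.

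1. **Estimand.** The study is about somatoform disorders as a class, and Analysis B pools everyone. If the question is only whether low-vagal patients have worse trait scores across this mixed population, a difference carried by diagnosis is a true difference and not a false positive. This stands. The rejection rates above are error rates only for an effect of vagal profile beyond diagnosis. The SAP does not say which question it asks, so both answers should be reported.

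2. **Size.** The documents give no HRV or trait figures by diagnosis. At 0.3 SD there is no visible inflation, and at 0.5 SD it is slight. This stands. A reader might infer that the profile findings will be disease differences; the documents support only that they could be.

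3. **Reach.** A reader might infer that all of Analysis C, or Analysis A as well, is confounded. Neither follows. A stable disease difference leaves the Analysis C interaction at its nominal level, and the planned 1:1 mix protects the Analysis A group contrast. Omitting diagnosis from A may cost precision and hides any difference in effect by disease, but it does not bias that contrast.

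4. **Remedy.** A full profile-by-diagnosis factorial would be fragile. With tone and flexibility independent within a disease, only about 20 to 23 of the 40 patients in Analysis C have concordant profiles. At a 0.8 SD vagal gap the smallest cell held two patients or fewer in 87% of runs. This stands and is why the fix uses additive terms.

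It is also fair that the sample size was set for HF vagal tone in a within-between ANOVA, so the trait t-tests are not what the trial was powered on. That limits the weight of the point without removing it.

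**Conclusion.** The omission is certain: diagnosis is a design variable and appears in no listed test, and nothing balances it across the K-means profiles. The consequence is conditional. The Analysis B trait comparison and the Analysis C profile main effect can reflect diagnosis if the diseases differ on both vagal measures and outcome. The Analysis C interaction needs the further condition of differential change from T2 to T3.

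Under the assumed gaps, the effect on Analysis B runs from none at 0.3 SD to roughly a threefold to fourfold rejection rate at 0.8 SD (17-19% against about 5%) and 30-36% at 1.0 SD. These figures rest on equal gaps for vagal measures and trait, comparison of concordant profiles, and 25 patients per disease. Confidence is high in the omission and low in the size. The change should be made, because the unadjusted result alone cannot show whether vagal profile adds anything to diagnosis.

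**What to change.** - **Analysis B:** replace the t-test by a linear model with profile and an additive diagnosis term. Keep the unadjusted comparison as a secondary description of the pooled population.
- **Analysis C:** add diagnosis and diagnosis-by-time as additive terms, without a profile-by-diagnosis factorial.
- **Both:** tabulate diagnosis by profile. This shows directly whether the problem has arisen.
- **Analysis A:** no change is needed to remove bias if the quotas are met.

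Cost: one degree of freedom in B; one for diagnosis and one more for diagnosis-by-time in C (two time points, so 2 − 1 = 1). Some precision is lost if profile and diagnosis are strongly related. No new data are needed, because diagnosis must be known to fill the quotas.
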